101 hypothesize that there is a moderate to strong positive correlation between the specificity of
102 the prompts and the quality of evidence-based health risk communication provided by LLMs.

103 3. Compare the evidence-based quality of responses generated by laypeople with varying levels
104 of informed prompting by comparing the quality of LLM responses based on prompts
105 generated by laypeople who provide varying levels of detail and information. We will assess
106 whether layperson-generated prompts result in more evidence-based responses than low-
107 informed prompts, but less so than moderately informed prompts.

108 RQ3: Are LLM responses generated by laypeople more evidence-based than those from low-
109 informed prompting, but less so than moderately informed prompting? We hypothesize that
110 Layperson-generated prompts produce more evidence-based responses compared to low-
111 informed prompts, but less so than moderately informed prompts that include about 50% of
112 key health decision-making information.

113 4. Evaluate the impact of a minimal boosting intervention on the quality of LLM responses by
114 assessing whether a minimal boosting intervention—where users are encouraged to provide
115 more specific prompts by considering the consequences of their health decisions—can
116 improve the evidence-based quality of LLM responses.

117 RQ4: Does a minimal boosting intervention increase evidence-based responses? We
118 hypothesize that reminding users to consider the consequences of their choices will lead to an
119 increase in evidence-based responses, improving the overall adherence of LLM outputs to
120 guideline-based communication standards.

121 5. Test the digital native hypothesis: RQ5: Without boosting intervention, digital natives (defined
122 as participants under 30 years of age) do not prompt a higher quality of LLM responses than
123 people from the age of 30 years and more.

124 **Trial Design**

125 The study is divided into two phases. Phase 1 uses a content analysis design to evaluate LLM responses
126 to standardized prompts. Phase 2 is a randomized between-subjects experiment with a 1:1 allocation
127 ratio, comparing standard prompting (control group) and enhanced prompting (intervention group).
128 Each group will interact with LLMs under similar conditions, but with differing levels of instruction
129 specificity.

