185 potential differences between LLMs with the help of ANOVA across repetitions. Two independent
186 researchers will code the data. Interrater reliability will be assessed using Cohen’s kappa coefficient to
187 evaluate agreement between the coders. Any discrepancies will be resolved through consensus
188 discussions to ensure consistent and accurate evaluation.

189 Phase 2:

190 Descriptive statistics will be calculated for the demographic variables gender, age, and education, as
191 well as for LLM usage frequency, prior experience, and preference for shared decision-making.

192 The primary analysis will focus on comparing the quality of LLM-generated responses across groups
193 using inference statistical methods for assessing differences between participants assigned to the
194 prompting conditions (independent variable). To evaluate the responses (the dependent variable) the
195 responses will be coded using two predefined scales to assess its adherence to evidence-based (EB)
196 health communication standards and pooled additionally (so, three dependent variables for
197 independent analyses). The coding will be based on the MappInfo tool for the evidence-based quality
198 assessment of digital health information¹⁶ and the Guideline for the Development of Evidence-based
199 Patient Information². The coding will be done by two independent raters, and inter-rater reliability will
200 be assessed using Cohen’s kappa. Any discrepancies between raters will be resolved through discussion
201 and consensus. The code book will be provided in the appendix of the final study.

202 Secondary analyses will include a statistical test based on age split (<30 vs 30+ years) on the difference
203 in the quality of LLM responses prompted by participants of the control condition and there will be an
204 assessment of participant preferences for informed decision-making processes and their experiences
205 with LLMs, using descriptive statistics and mean comparisons. A subgroup analysis will explore
206 potential differences in responses based on demographic characteristics.

207 All statistical tests will be conducted at a significance level of $p < .050$ (and adjusted downwards
208 according to Bonferroni procedure for multiple testing), and effect sizes will be calculated to determine
209 the meaning of findings. Results will be presented in detail with supporting tables and figures.

210 **Inclusion Criteria**

211 Phase 1, LLMs:

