278 Expert scoring of how evidence-based LLM communication is (mappInfo tool in addition to a novel
279 score based on the guideline EB health information)

280 Secondary Outcome:

281 Self-reported use and experience with LLM; preference in shared decision-making

282 **Sample Size**

283 Phase 1:

284 There are no human participants involved.

285 Phase 2:

286 To analyze a moderate ANOVA main effect (partial eta squared = .06) comparing two between-subjects
287 conditions (with and without intervention), we are aiming for a minimum sample size of n= 237

288 participants. To ensure a representative sample reflecting the simplified census data of Great Britain in
289 terms of sex, age, and ethnicity, we will recruit $n = 300$ participants from a diverse pool via Prolific²⁰.

290 **Recruitment**

291 Participants will be recruited via the online platform Prolific²⁰.

292 **Assignment of Interventions**

293 Participants will be assigned to either the control group or the intervention group via block
294 randomization. In the intervention group, participants will receive additional instructions designed to
295 improve the quality of the prompts they generate for the LLMs.

296 **Allocation**

297 To achieve a balanced distribution of participants across the study groups, we will employ a block
298 randomization (1:1 allocation ratio) with the BLOCKRAND() function in SoSci Survey. The assignment
299 is concealed by this function.

300 **Blinding**

301 Participants and researchers will be blinded to both the assigned LLM and the type of prompting
302 instructions to prevent any bias in interaction and response evaluation. Coding will happen
303 independently by two researchers.

304 **Data Management**

305 Data will be collected via the SoSci Survey platform, and all datasets will be anonymized and stored
306 securely on password-protected servers to ensure participant confidentiality. Contact details will not
307 be collected, as Prolific—responsible for participant recruitment—operates with an anonymized data
308 collection model. Participant demographic data, such as gender and age, will be collected separately
309 within the study, despite these being part of the quota set by Prolific.

310 Data handling is fully anonymized. Prolific manages recruitment, while SoSci Survey, hosted by the
311 University of Potsdam, handles the questionnaires. Communication with the LLMs is facilitated through

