312 an API within SoSci Survey, and LLM providers do not have access to the study data. Payment processing
313 is managed entirely by prolific.co, and no financial data is collected or stored on our end. Additionally,
314 no names, addresses, birth dates, or IP addresses will be recorded. We will not record the recruitment
315 IDs generated by prolific.co, and due to the large number of simultaneous participants and the
316 variability in time between recruitment and survey completion, it will not be feasible to link
317 questionnaire responses with recruitment IDs.

318 The anonymized research data will initially be stored on a password-protected account under the
319 control of the project lead on the SoSci Survey server (hosted by the University of Potsdam). For further
320 analysis, the data will be transferred to password-protected computers under the supervision of project
321 team members at the Harding Center for Risk Literacy. Prolific will not have access to the research data
322 at any point.

323 **Statistical Methods**

324 Data will be analyzed using descriptive statistics and inferential statistical tests, including t-tests and
325 ANOVA for group comparisons, and linear regression models for more detailed analyses of prompt
326 specificity effects. All statistical tests will be conducted at a significance level of $p < 0.05$, and effect sizes
327 will be calculated to determine the practical significance of findings.

328 **Harms**

329 No physical or psychological risks are anticipated for participants. Anticipated survey completion time
330 is six minutes. Participation is entirely voluntary, and participants can withdraw at any time.

331 Errors of the used LLMs will be identified through content analysis conducted by independent human
332 raters using predefined quality metrics, and categorized based on their nature and impact on the
333 reliability of the information provided. The errors will then be analyzed to determine patterns of LLM
334 performance issues. If errors are not analyzed in specific instances, it will be due to limitations in the
335 scope of the study, such as focusing primarily on guideline adherence rather than linguistic or technical
336 issues outside the study's objectives.

337 **Monitoring**

338 The study will be monitored by the research team at the Harding Center for Risk Literacy. Regular audits
339 will be conducted to ensure compliance with the study protocol and data management procedures.

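### RQ5 claims that under-30s have no advantage, but its only analysis is a difference test, which can contradict that claim but not support it when non-significant

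*Protocol*

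**What the plan says.** The Objective section lists RQ5 as the fifth aim, a test of the digital native hypothesis. It is worded as the absence of an advantage: without the intervention, digital natives (defined "as participants under 30 years of age) do not prompt a higher quality of LLM responses than" their elders).

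The Phase 2 part of the Analysis section supplies the method: "Secondary analyses will include a statistical test based on age split (<30 vs 30+ years) on the difference", which continues "in the quality of LLM responses prompted by participants of the control condition and there will be an" assessment of preferences and LLM experience. The comparison therefore uses the control arm only.

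On error rates, the same section says: "All statistical tests will be conducted at a significance level of $p < .050$ (and adjusted downwards" by a Bonferroni procedure for multiple testing). The number of tests is not given. The Statistical Methods section repeats the .05 level without mentioning an adjustment and names the tools: "Data will be analyzed using descriptive statistics and inferential statistical tests, including t-tests and" ANOVA, plus linear regression. Effect sizes are to be calculated, but nothing links them to a decision on RQ5.

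The only sample-size reasoning concerns the boosting effect: "To analyze a moderate ANOVA main effect (partial eta squared = .06) comparing two between-subjects" groups. No margin, equivalence or non-superiority test, or confidence-interval rule appears for RQ5.

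**The concern.** The hypothesis and the test face opposite ways. RQ5 says that an advantage is absent. A difference test takes that absence, or something close to it, as its null hypothesis and asks whether the data contradict it. A significant result favouring the under-30s would count against RQ5. Short of a significant result favouring the older group, no outcome of the test counts as evidence for RQ5. Non-significance is compatible both with no advantage and with a real advantage that the comparison was too imprecise to detect.

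Two features of the plan sharpen this. The comparison sits in one arm and is split at age 30, so the younger group may be small. And lowering alpha is cautious when the aim is to show a difference, but here it makes the outcome that appears to agree with RQ5 more likely. What is at stake is a statement about digital natives that the data could not carry.

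**Working it through.** **The plan's own figures.** No size or power figure is given for RQ5, so there is none to reproduce. The sample-size paragraph states "conditions (with and without intervention), we are aiming for a minimum sample size of n= 237" for the boosting effect, and then "terms of sex, age, and ethnicity, we will recruit $n = 300$ participants from a diverse pool via Prolific". Partial eta squared .06 gives f = sqrt(.06/.94) = 0.2526, which for two equal groups is d = 2f = 0.505. This is the only effect size in the protocol, and it concerns boosting, not age. The figure of 237 is not at issue here.

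**Inputs.**
- Controls: 300 randomised 1:1 gives about 150.
- Under-30 share: not stated. Assumed 15%, 20% or 25%, which gives 22 vs 128, 30 vs 120 or 38 vs 112.
- Sidedness: not stated. Both are shown.
- Alpha: .05, and .05/3 as an assumed Bonferroni level. The divisor is not stated; three reflects the three dependent variables in the Analysis section.

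**Precision.** In SD units, SE = sqrt(1/n1 + 1/n2), and the 95% half-width is t(148 df) × SE with t = 1.976.
- 22 vs 128: SE 0.231, half-width 0.46
- 30 vs 120: SE 0.204, half-width 0.40
- 38 vs 112: SE 0.188, half-width 0.37

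**Chance of a non-significant result when the under-30s truly are better.** This is 1 minus the power of the noncentral t test with 148 df and noncentrality d/SE. For 30 vs 120 and d = 0.3, the noncentrality is 0.3/0.204 = 1.47 and two-sided power at .05 is .309, so the advantage is missed 69% of the time.

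| Test | True advantage | 15% share | 20% share | 25% share |
|---|---|---|---|---|
| Two-sided .05 | 0.3 SD | 75% | 69% | 65% |
| Two-sided .05 | 0.5 SD | 42% | 32% | 25% |
| Two-sided .05/3 | 0.3 SD | 87% | 83% | 79% |
| Two-sided .05/3 | 0.5 SD | 60% | 49% | 40% |
| One-sided .05 | 0.3 SD | 64% | 57% | 52% |
| One-sided .05 | 0.5 SD | 30% | 21% | 16% |

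The step from .05 to .05/3 shows the direction of the Bonferroni effect: every miss rate rises.

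**What a test that fits RQ5 could deliver.** Take a one-sided .05 non-superiority test with margin M and no true difference. Its power is Phi(M/SE − 1.645). For 30 vs 120 and M = 0.5, this is Phi(2.449 − 1.645) = Phi(0.804) = .79.

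| Margin | 15% share | 20% share | 25% share |
|---|---|---|---|
| 0.5 SD | 70% | 79% | 85% |
| 0.3 SD | 37% | 43% | 48% |
| 0.2 SD | 22% | 25% | 28% |

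At a 20% share, 80% power would need about 155 controls for a 0.5 SD margin, 430 for 0.3 SD and 967 for 0.2 SD. The planned control arm can therefore support RQ5 only against a wide margin.

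**The case against.** The strongest reply is that the protocol nowhere says that a p-value above alpha will count as confirmation. The aim is headed as a test of a hypothesis, and a difference test is a coherent way to expose that hypothesis to refutation. Effect sizes are also promised as an aid to interpretation. This stands in part: the misreading is left open, not prescribed. But a promised effect size is not a decision rule, and the plan gives no other route to a conclusion on RQ5.

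A second reply is that the numbers rest on assumptions. This also stands. The under-30 share, the sidedness and the Bonferroni divisor are not in the protocol, and the Statistical Methods section does not repeat the adjustment. RQ5 is directional, and a one-sided test lowers the miss rates. The mismatch between claim and test depends on none of these inputs.

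A third reply is that a separate statistical analysis plan may settle the test. It could fix the form and the sidedness. But the protocol already fixes the hypothesis and the kind of test, and choosing between a t-test and ANOVA would not make them fit.

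A reader might infer that the trial would probably report the digital-native advantage as refuted even when a relevant one exists. The documents do not support that. At 0.5 SD the two-sided .05 miss rate is below one half across the assumed shares, and one-sided it is 16-30%. It passes one half only when a stricter assumed alpha is combined with a low assumed share. Nor does the protocol establish that few participants are under 30; it gives no share.

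**Conclusion.** The point holds in a limited form. RQ5 is a no-advantage claim paired with a test that can contradict it but whose non-significance cannot support it, and the plan has no safeguard against reading non-significance as support. This follows from the wording alone.

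Its practical size is illustrative. With 15-25% of about 150 controls under 30, an advantage of 0.3 SD would more often than not go undetected under every test form shown. For 0.5 SD the result depends on share, sidedness and alpha, and ranges from 16% to 60%.

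Severity is moderate. The age split is a secondary, non-randomised comparison within one arm, and neither the primary boosting comparison nor its sample size is affected.

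**What to change.** In the secondary-analysis paragraph of the Analysis section, state three things:

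1. RQ5 is judged on the estimated difference in quality score (under 30 minus 30 or more) in the control arm, with its confidence interval.
2. A non-significant difference is not support for RQ5.
3. RQ5 may be claimed only if the upper one-sided 95% limit lies below a margin that the sponsor fixes and justifies before analysis. Otherwise it is reported as exploratory or inconclusive.

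The margin needs its own argument. The 0.5 SD implied by the boosting calculation is one candidate, but nothing in the protocol says that an age gap of that size is negligible. If no margin can be defended, declaring RQ5 exploratory and reporting the estimate with its interval is enough.

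The cost is a few sentences of protocol text and one confidence interval, with no extra participants. The downside is that RQ5 may end without a conclusion: with no true difference, power is about 70-85% at a 0.5 SD margin but only 37-48% at 0.3 SD. The change should be made before the data are seen, because a margin chosen afterwards would carry little weight.

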245 responses will be excluded.

246 Phase 2, Participants:

248 The exclusion criteria for selecting the Participants in the study will be the following:

- 249 - Health Professionals: Individuals with professional expertise in healthcare, particularly in
250 cancer screening or health communication, will be excluded to avoid bias and ensure that
251 participants reflect the general lay population.
252 - Previous Experience with LLM Studies: Participants who have taken part in similar studies
253 involving LLMs will be excluded to prevent familiarity with the technology from influencing the
254 results.

255 **Procedure and material**

256 Phase 1:

257 Researchers will prompt LLMs via API and collect the responses.

258 Phase 2:

259 Participants will receive a brief introduction outlining the study's purpose, which involves interacting
260 with one of three LLMs [OpenAI ChatGPT (gpt-3.5-turbo)¹⁷, Google Gemini (1.5-Flash)¹⁸, or Mistral AI
261 Le Chat (mistral-large-2402)]¹⁹, all preset as a "helpful assistant" to obtain health information of either
262 BC or PC screening. Following informed consent, participants will be asked to provide basic
263 demographic details such as gender, age, and education level through a questionnaire interface built
264 with SoSci Survey. They will then be given the choice to receive information about either BC or PC
265 screening. Participants will engage with the chatbot by entering their queries (prompts) through the
266 LLM's API, and the generated responses will be collected alongside the prompts for systematic analysis.
267 At the end of the session, participants will be asked about their frequency of LLM usage, their prior
268 experience with such models, and their perspectives on how an informed decision-making process
269 should ideally be conducted for them, by choosing one from four options.

270 A pre-test with n=20 participants will be conducted to verify the effectiveness of the randomization
271 procedures, ensuring balanced group assignment, the technical functionality of the survey platform
272 and its integration with the LLM APIs. Additionally, the average completion time will be measured and
273 potential issues related to participant burden will be identified. Feedback on user experience will be
274 collected to address any usability concerns. Based on these findings, necessary adjustments will be
275 made at the protocol for the main trial.

276 **Tests and Outcomes**

277 Primary Outcome:

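### A one-of-four preference item falls under mean comparisons, and prior LLM use, asked only after the chat, is listed as an outcome (low priority)

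*Protocol*

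**What the plan says.** Four places in the protocol bear on this; the SAP is not at hand.

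- **Analysis, Phase 2 (secondary analyses):** there will be an "assessment of participant preferences for informed decision-making processes and their experiences" "with LLMs, using descriptive statistics and mean comparisons. A subgroup analysis will explore" demographic differences. Two variables and two methods share one clause.
- **Procedure and material, Phase 2:** gender, age and education are collected after consent and before the chat. Then: "At the end of the session, participants will be asked about their frequency of LLM usage, their prior" experience, and their view of how an informed decision-making process "should ideally be conducted for them, by choosing one from four options".
- **Tests and Outcomes:** the secondary outcome is "Self-reported use and experience with LLM; preference in shared decision-making".
- **Analysis, Phase 2 (opening sentence):** descriptive statistics are planned for the demographic variables, "well as for LLM usage frequency, prior experience, and preference for shared decision-making". Here the same three variables describe the sample.

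The Statistical Methods section names t-tests, "ANOVA for group comparisons, and linear regression models for more detailed analyses of prompt" specificity effects. It names no method for a categorical outcome.

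**The concern.** There are two separate problems.

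**Scale and method.** A single choice among four unscored options is a nominal variable. If the planned mean comparison is applied to it, the result depends on which option is numbered 1, 2, 3 or 4. A real shift between options could disappear, or change size and sign, through numbering alone.

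**Timing and label.** How often someone used LLMs before the study, and what experience they had, is settled before they see the boosting text. A session of about six minutes (Harms section) cannot alter that history; at most it can alter how it is reported. A difference between arms on these items would therefore reflect chance or reporting, not an effect of the intervention, so they do not serve as outcomes. Because they are collected after the boosting text and the chat, they are also less secure as descriptors of the sample, which is the other role the protocol gives them. The Exclusion Criteria already treat familiarity with LLMs as something that could influence results, since participants of similar studies are excluded for that reason.

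**Working it through.** The protocol gives no figure to reproduce on this point. The check sets the sections side by side and then illustrates the consequence of averaging option codes.

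**Step 1: reading the sections together.**

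| Item | When asked | Form | Status in Tests and Outcomes | Status in Analysis |
|---|---|---|---|---|
| Decision-making preference | End of session | One of four options | Secondary outcome | Descriptor; also in the mean-comparison clause |
| LLM use frequency | End of session | Not stated | Secondary outcome | Descriptor |
| Prior LLM experience | End of session | Not stated | Secondary outcome | Descriptor; also in the mean-comparison clause |
| Gender, age, education | Before the chat | Questionnaire | Not an outcome | Descriptor |

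The protocol speaks of informed decision-making in one place and shared decision-making in another. I take these to be the same item, since only one is described.

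**Step 2: numbering (assumed proportions).** Inputs: n = 150 per arm (300 recruited, 1:1); alpha 0.05 before any Bonferroni reduction; option shares are my assumption.

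*Example A.* Control 25/25/25/25%, intervention 35/15/15/35%, options coded 1 to 4.
- Control mean: 0.25 × (1 + 2 + 3 + 4) = 2.5
- Intervention mean: 0.35×1 + 0.15×2 + 0.15×3 + 0.35×4 = 2.5
- The mean comparison therefore has nothing to detect beyond its 5% false-positive rate.
- Chi-square, 3 df, noncentrality = n × Σ over both arms of (p − p̄)²/p̄, with average shares p̄ = 0.30, 0.20, 0.20, 0.30. Each arm contributes 2×0.0025/0.30 + 2×0.0025/0.20 = 0.04167, so the noncentrality is 150 × 2 × 0.04167 = 12.5. Power is about 86%.

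*Example B.* Control 25/25/25/25%, intervention 40/25/10/25%.
- The difference in means is 0.15 × (code of option 1 − code of option 3). Its size is 0.15 if the two codes are adjacent and 0.45 if they are 1 and 4, and its sign follows the numbering.
- Over all 24 numberings, power (normal approximation) runs from 19.7% (difference 0.15) to 95.3% (difference 0.45).
- Chi-square: 150 × 2 × (0.075²/0.325 + 0.075²/0.175) = 150 × 2 × 0.04945 = 14.8. Power is about 91% under every numbering.

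**Step 3: value of a pre-exposure covariate (assumed correlations).** If LLM-use frequency correlates r with the quality score within arms, adjustment multiplies the effective sample size by 1/(1 − r²).
- r = 0.2: 1/0.96 = 1.04, about 4%
- r = 0.3: 1/0.91 = 1.10, about 10%, or roughly 30 participants on 300

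The protocol gives no such correlation, so these show a range and are not estimates.

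**The case against.** The strongest reply concerns the clause on mean comparisons. It joins two variables to two methods, and a reader could sensibly take it as descriptive statistics for the categorical preference and means for LLM experience. It could also mean comparing mean quality scores across the four preference groups, which is valid for a nominal variable. No sentence says that codes 1 to 4 are averaged, and none announces a test of preference between arms. The list in Statistical Methods is introduced as non-exhaustive, and naming a chi-square test for one secondary item can be left to an SAP. If the four options are in fact ordered, a mean is less wrong. All of this stands, and it makes the first part a matter of clarifying an ambiguous clause. But the text does not select the lenient reading, and it states no order for the options.

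On timing, asking about LLM habits at the end keeps those questions from priming the prompts, which drive the primary outcome. That is a fair trade-off, though any priming from an earlier question would be equal in both arms. Distortion of the answers by the session is possible but not shown. Neither argument explains why a pre-existing trait is listed as an outcome.

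A reader might also infer that the protocol spoils a planned covariate or subgroup variable. The documents do not support that. The subgroup analysis is tied to demographic characteristics, and LLM use is nowhere proposed for adjustment. The absence of an adjustment model is not a defect of this protocol.

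**Conclusion.** The point holds in limited form. As written, the secondary-analysis clause puts an unscored one-of-four choice under mean comparisons. Separately, the outcome list includes LLM use and prior experience, which predate the study and are measured only after exposure, while the Analysis section also treats them as descriptors.

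The size is modest. The power figures of 20% to 95% against 91%, and 86% for the example with equal means, rest on assumed option shares, a between-arm comparison the protocol does not explicitly announce, and numeric coding it does not specify. They show the consequence of the literal reading and do not predict this trial's data. The possible precision gain of 4% to 10% rests on assumed correlations.

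A reader might infer that the main result is at risk or the trial too small. Neither follows. The randomised primary comparison of response quality uses none of these items and remains valid, and recruitment of 300 exceeds the stated minimum of 237. The priority is low.

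**What to change.** 1. In the Phase 2 secondary analyses, state that the four-option preference is reported as the proportion choosing each option, and that any group comparison uses a chi-square or Fisher test. Limit mean comparisons to items with a scale.
2. Move the LLM-use and prior-experience items to the existing demographics page before the chat. Remove them from the secondary outcomes and list them as baseline characteristics. The preference item can stay at the end.
3. Optional: once it is measured before exposure, LLM-use frequency may be prespecified as a covariate in the primary model. This is an efficiency choice, not a correction.

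The cost is a change of page order in the survey and two or three sentences. The downside is slight priming from asking about LLM habits first, equal in both arms. The pre-test with 20 participants, after which the protocol already foresees adjustments, is a convenient point to check the new order. The page order has to be settled before the main data are collected, because an SAP cannot correct it afterwards.

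### Bonferroni is valid for the three Phase 2 scores, but Holm's step-down procedure gives the same family-wise protection and somewhat more power per score at no cost

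*Protocol*

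**What the plan says.** In the protocol's Analysis section, Phase 2, the LLM responses are coded on two scales (MappInfo and a score based on the patient-information guideline). A third score combines them: "health communication standards and pooled additionally (so, three dependent variables for" separate analyses. The same section sets the level and the correction: "All statistical tests will be conducted at a significance level of $p < .050$ (and adjusted downwards" "according to Bonferroni procedure for multiple testing". The sentence covers every test. It does not say which tests form a family or what the divisor is.

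The Statistical Methods section gives the level again, this time with no adjustment: "specificity effects. All statistical tests will be conducted at a significance level of $p < 0.05$, and effect sizes".

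The Sample Size section plans for one effect: "To analyze a moderate ANOVA main effect (partial eta squared = .06) comparing two between-subjects" conditions. It continues "we are aiming for a minimum sample size of n= 237" and then "we will recruit $n = 300$ participants from a diverse pool via Prolific". It states neither the significance level nor the power.

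**The concern.** The protocol itself names the correction, so the choice is not left to a statistical analysis plan. Plain Bonferroni holds every score to the same strict threshold, whatever the other scores show. Holm starts at that threshold and relaxes it after each rejection, with the same guarantee on family-wise error.

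At stake is the reading of RQ4, the only randomised comparison. Three scores will be reported side by side. With Bonferroni, one score can narrowly miss its threshold while the other two pass, and the result looks mixed. Under Holm some of these cases become a consistent result.

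**Working it through.** **Inputs from the protocol.** Partial eta squared .06; 1:1 allocation; minimum N 237; recruited N 300; three scores, the third a pool of the first two; nominal level .05.

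**Assumptions, not in the protocol.** The family is the three RQ4 scores, so the Bonferroni level is .05/3 = .0167. The correlation r between the scales is 0.3 to 0.7. The pooled score is the standardised sum of the two scales. The true effect is the same on both scales. Tests are two-sided.

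**Step 1: the effect.** f = √(.06/.94) = 0.2526, and d = 2f = 0.505.

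**Step 2: the planned sample size.** I used noncentral F power with 1 and N − 2 degrees of freedom and noncentrality f²N. At level .05, 80/90/95% power needs N = 125/167/206. At .05/3 it needs 167/215/259. At .01 it needs 187/237/283. The figure of 237 is matched exactly by level .01 (= .05/5) with 90% power: power is 90.1% at N = 237 and 89.9% at N = 236. The protocol states neither value, so this is an inference. It suggests that a correction may already be paid for.

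**Step 3: one scale under Bonferroni.** The expected z is d√N/2, and the critical value at .0167 two-sided is 2.394.
- N = 237: 0.505 × √237 / 2 = 3.889; 3.889 − 2.394 = 1.495; power 93.3%.
- N = 300: 0.505 × √300 / 2 = 4.376; 4.376 − 2.394 = 1.982; power 97.6%.

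The exact F test gives 92.9% and 97.5%.

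**Step 4: why Holm never rejects less.** Holm orders the three p-values and compares the smallest with .05/3, the next with .05/2 and the largest with .05, stopping at the first failure. A p-value at or below .05/3 therefore passes under both methods. Whether anything is rejected at all depends on the smallest p-value and the same threshold, so power for at least one score is identical.

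**Step 5: simulation at the planned effect** (normal approximation, 1,000,000 replicates per setting; Bonferroni → Holm).

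| N | r | Power per scale | All three scores | At least one (both methods) |
|---|---|---|---|---|
| 237 | 0.3 | 93.2% → 97.0% | 87.6% → 94.8% | 99.4% |
| 237 | 0.5 | 93.2% → 96.7% | 88.3% → 94.9% | 98.7% |
| 237 | 0.7 | 93.3% → 96.3% | 89.4% → 95.1% | 97.5% |
| 300 | 0.3 | 97.6% → 99.2% | 95.5% → 98.4% | 99.9% |
| 300 | 0.5 | 97.6% → 99.1% | 95.7% → 98.5% | 99.7% |
| 300 | 0.7 | 97.6% → 98.9% | 96.0% → 98.5% | 99.3% |

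The chance of a mixed result is the last column minus the one before it. At N = 237 and r = 0.5 it is about 10% with Bonferroni and 4% with Holm.

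**Step 6: a smaller effect.** At N = 300 and d = 0.25 (about half the planned effect), power per scale rises from about 41% to 51%, 50% and 49% for r = 0.3, 0.5 and 0.7. Power for all three rises from 21% to 37%, from 25% to 40% and from 29% to 43%.

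**Step 7: error under the global null.** Family-wise error is the same for both methods: about 3.8%, 3.4% and 3.0% for r = 0.3, 0.5 and 0.7. All are below 5%.

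**The case against.** The strongest reply is that Bonferroni is valid under any dependence, including for a pooled score, so the protocol says nothing wrong. At the planned effect with 300 participants the gain is about 1.5 points per scale, the chance of at least one significant score is untouched, and the protocol never makes success on all three scores a criterion. All of this stands. It limits the point to a small improvement but does not remove it, because the gain costs nothing in error control.

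The family is also an assumption. The sentence on the correction gives no divisor, so .05/3 is my reading, and another family would change the figures.

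A reader might infer more than the protocol supports:
- *That Holm's gain comes from the correlation with the pooled score.* It does not. Holm ignores correlation and its gain shrinks as correlation rises. At N = 300 and d = 0.35 (an illustrative effect), the gain per scale is 9.4 points at r = 0.3, 7.4 at 0.7, 5.0 at 0.9 and 1.8 at 0.99. Nor does Holm recover the unused error in Step 7.
- *That the protocol claims the three tests are statistically independent.* Its wording most naturally means three separate analyses.
- *That alpha is split between the two RQ3 contrasts.* The Objective section, item 3, gives only the hypothesis that lay prompts do better than low-"informed prompts, but less so than moderately informed prompts that include about 50% of" the key information. No section states a split or specifies the test.
- *That any mixed result would come only from the correction.* Scores can also disagree through sampling error or real differences between the scales.

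**Conclusion.** The point holds as a minor, free improvement. Bonferroni is valid here, but Holm gives the same family-wise guarantee and rejects at least as much. At the planned effect the gain per scale is 3 to 4 points at the minimum sample size and about 1.5 points at the recruited one. For all three scores together it is about 6 to 7 points and 2.5 to 3 points. The gain is larger if the true effect is smaller than planned. These sizes rest on a three-score family, a between-scale correlation of 0.3 to 0.7 and equal effects on both scales. That Holm never rejects less needs none of these assumptions.

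Whether any adjustment applies at all, given the unadjusted level in the Statistical Methods section, is a separate question that this point does not settle.

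**What to change.** In the Analysis section, replace the Bonferroni procedure with the Holm step-down procedure, and state that it applies to the three RQ4 scores as one family (ordered p-values against .05/3, .05/2 and .05).

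Optionally, if the correction is meant to reach RQ3, state that RQ3 is supported only when both directional contrasts are significant, each at the full level. Because the claim needs both, dividing alpha between them adds no protection.

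The cost is one sentence, with no new data and no looser error control. The one drawback is that simultaneous confidence intervals are less simple under Holm, and the protocol plans none.
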